### 7.1. Subject Inclusion Criteria

An included subject will be or have:

1. Aged 2 to 17 years, inclusive, as of the time of consent.
2. Written informed consent from parent(s) or legal guardian(s) and assent from the child when appropriate, as determined by the Institutional Review Board (IRB), consistent with regulatory criteria and requirements.
3. Sufficient healthy skin identified and reserved as a donor site in the event that the StrataGraft treatment site(s) requires autografting.
4. Thermal burns of no more than 30% TBSA.
5. Consenting adult(s) is/are able and willing to attend/bring child to the scheduled visits and comply with study procedures.
6. Study treatment area(s) that is/are: a) DPT in depth (ie, containing dermal elements) and for which excision and autografting are clinically indicated, as assessed by the investigator, and b) located on the torso or extremities.
7. Study treatment area of 0.5% to 10% TBSA, which may be composed of up to 3 non-contiguous areas located on the same extremity or plane of the torso.

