### 12.3. Statistical Analyses

This section provides a general summary of the statistical methods to be used in analyzing study data. A more detailed statistical analysis plan (SAP) will be provided in a separate document that will be finalized prior to database lock. SAS version 9.4 or newer will be used.

Descriptive statistics for continuous variables will include the mean, median, standard deviation, minimum value, and maximum value. Categorical data will be summarized by counts and percentages.

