#### 12.3.1. Efficacy Analyses

##### 12.3.1.1. Primary Endpoint

The pediatric study plans to enroll up to 50 subjects into two age cohorts: 2 to  $\leq$  12 years and 12 to  $\leq$  17 years. Endpoints will be assessed using the entire ITT population.

The primary efficacy endpoint for this study the percentage of subjects achieving confirmed complete closure of all StrataGraft treatment sites on or before Week 12 without autograft placement. For subjects with more than one treatment site, all treatment sites must be confirmed closed before the subject can be declared to be confirmed closed. Confirmed complete wound closure is defined as complete skin re-epithelialization confirmed at 2 consecutive visits at least 2 weeks apart but no later than Week 20. Complete confirmed wound closure will be considered to have occurred at the earlier of the two observations of complete skin re-epithelialization without drainage.

For the primary efficacy endpoint, number (%) and 95% Confidence Interval (CI) derived from the normal approximation to the binomial will be summarized based on the ITT population. Subjects with missing data will be imputed as non-responders. The statistical significance for the primary endpoint is declared if the lower limit of the 95% CI of the endpoint is  $\geq 50\%$ .

The analysis will also be performed based on all observed data, i.e, excluding any missing data. The analyses by age cohort will be presented.

The Objective, Population, Hypothesis, Endpoint, and Intercurrent Events and Data Handling for the Primary Endpoint are described in [Table 7](#).

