### 12.3.1.2. Ranked Secondary Endpoints

After the primary endpoint is successfully reached, the ranked secondary efficacy endpoints will each be tested with a 2-sided confidence interval with 0.05 Type I error in a hierarchical manner in the rank order as in [Table 8](#). The ranked secondary endpoints are:

1. Mean of averaged percent area of StrataGraft treatment site closed per subject at Week 12 without autograft placement
2. Number (%) of confirmed complete wound closures of the StrataGraft treatment sites on or before Week 12 without autograft placement
3. Mean of averaged percent area of StrataGraft treatment site autografted by Week 12

For continuous efficacy endpoints, missing data will not be imputed. Missing or incomplete binary variables will be imputed as failures. Missing data are anticipated to occur only if the subject is lost to follow-up because information can be obtained for a missing visit when the subject returns for a subsequent visit. If a subject has autograft placement, the data collected after the autograft placement will be censored.

The averaged percent area closed per subject at Week 12 will be calculated as (Sum of percent area closed across treatment sites for a subject at Week 12/the total number of treatment sites on a subject).

The percentage of StrataGraft treatment sites with confirmed complete wound closure on or before Week 12 will be calculated as [(Total number of StrataGraft treatment sites with confirmed complete wound closure without autografting on or before Week 12/Total number of treatment sites) x 100].

The averaged percent area of StrataGraft treatment sites per subject autografted by Week 12 will be calculated as (Sum of percent area of StrataGraft treatment sites per subject autografted by Week 12/the number of treatment sites on that subject). It is a cumulative sum of percent area autografted for all nonmissing visits on or before Week 12.

The summary statistics with 95% confidence interval (CI) and p-value based on null hypothesis specified in [Table 8](#) for each endpoint from t-distribution will be presented based on the ITT population by designated treatment site and pooled designated treatment site. The analyses by age cohort will be presented.

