### 12.3.1.3. Binary Endpoints

For binary endpoints, number (%) of subjects and its 95% CI derived from the normal approximation to the binomial will be summarized based on ITT by designated treatment site and pooled designated treatment site. The denominator for a treatment site is determined by numbers of subjects with the designated site. The number and percent of missing data will be shown.

The missing data of binary endpoints will not be imputed for exploratory endpoints.

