To evaluate the number (%) of StrataGraft treatment sites with confirmed complete wound closure without autograft placement on or before Week 12	All enrolled subjects who received StrataGraft	$H_{02}$ : The response rate of StrataGraft treatment sites with confirmed complete wound closure without autograft placement on or before Week 12 is less than or equal to the 50% $H_{12}$ : The response rate of StrataGraft treatment Sites with confirmed complete wound closure without autograft placement on or before Week 12 is greater than the 50%	Number (%) of StrataGraft treatment sites with confirmed complete wound closure without autograft placement on or before Week 12	
Missing/incomplete binary variable will be imputed as failure.

Objectives	Population	Hypotheses	Endpoints	Intercurrent events and data handling
To evaluate the mean averaged percent area of StrataGraft treatment sites autografted per subject by Week 12	All enrolled subjects who received StrataGraft	$H_{02}$ : Mean of averaged percent area of StrataGraft treatment sites autografted per subject by Week 12 $>50\%$ . $H_{12}$ : Mean of averaged percent area of StrataGraft treatment sites autografted per subject by Week 12 $<50\%$ .	Mean of averaged percent area of StrataGraft treatment sites per subject autografted by Week 12	

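### The pooled interval and p-value for the second ranked secondary count treatment sites, up to three per child, with no allowance for correlation within a child

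*Combined protocol and SAP*

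**What the plan says.** A child's study area "may be composed of up to 3 non-contiguous areas located on the same extremity or plane of the torso" (protocol 7.1, item 7), so a child contributes one, two or three sites.

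The second ranked secondary is a percentage of sites: "Total number of StrataGraft treatment sites with confirmed complete wound closure without autografting on or before Week 12/Total number of treatment sites" (12.3.1.2; the Synopsis has the same formula). Table 8 tests "The response rate of StrataGraft treatment sites with confirmed complete wound closure without autograft placement on or before Week 12" against 50%, as a step in the hierarchy that follows the primary.

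Two methods could apply to it:

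- Section 12.3.1.2 gives an interval and p-value "for each endpoint from t-distribution will be presented based on the ITT population by designated treatment site and pooled designated treatment site".
- Section 12.3.1.3 counts subjects for each binary endpoint and says of the percentage: "its 95% CI derived from the normal approximation to the binomial will be summarized based on ITT by designated treatment site". The same summary is planned over all sites combined. On denominators it adds: "The denominator for a treatment site is determined by numbers of subjects with the designated site".

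Neither mentions clustering, a robust variance or a design effect. Section 12.3 defers detail: "A more detailed statistical analysis plan (SAP) will be provided in a separate document". The SAP is a memo recording that one subject was enrolled, that no formal analysis will be done, and that only listings will be produced.

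On missing data, the Synopsis, 12.3.1.2 and Table 8 count a missing binary outcome as a failure. Section 12.3.3 says that missing data for the ranked secondaries are left unimputed, without excepting the binary one.

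**The concern.** Sites on one child share the host, the injury, the operation, the wound care and the follow-up, so their outcomes are plausibly positively correlated. An interval that treats them as independent then overstates the information: it is too narrow and its p-value too small.

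The protocol handles multiple sites elsewhere. For the primary, "all treatment sites must be confirmed closed before the subject can be declared to be confirmed closed", and the first and third ranked secondaries average within the child before analysis. By-site summaries have at most one observation per child. Only the pooled result for the second ranked secondary is exposed. There the unit is also unsettled, because 12.3.1.3 speaks of subjects while the endpoint counts sites.

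**Working it through.** **1. The plan's own figure.** Section 12.1 states more than 90% power for the subject-level primary with 50 children, a null of 50% and a true rate of 83%. The normal-approximation lower limit reaches 50% at 32/50 (0.64 − 1.96√(0.64×0.36/50) = 0.507) but not at 31/50 (0.485). Then P(X ≥ 32 | 50, 0.83) = 0.9997. The stated power is confirmed. No power is stated for the second ranked secondary.

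**2. Assumptions.** The documents give neither the number of sites per child nor the intraclass correlation (ICC), so both are varied. The 83% is the plan's subject-level rate, used here as a site rate. The t interval is read as treating sites as independent with sites − 1 degrees of freedom. That is also an assumption, because the text gives no variance unit or degrees of freedom.

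**3. Variance inflation.** With k sites per child, the design effect is 1 + (Σk²/Σk − 1)×ICC.

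| Children with 1/2/3 sites | Σk | Σk² | Design effect, ICC 0.3 to 0.7 | Square root |
|---|---|---|---|---|
| 40/8/2 | 62 | 90 | 1.14 to 1.32 | 1.07 to 1.15 |
| 30/12/8 | 78 | 150 | 1.28 to 1.65 | 1.13 to 1.28 |
| two each | 100 | 200 | 1.30 to 1.70 | 1.14 to 1.30 |
| three each | 150 | 450 | 1.60 to 2.40 | 1.26 to 1.55 |

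**4. The two intervals.** With n sites, m children, y closed sites in a child and p = Σy/n:

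- Unadjusted: p ± t(n−1)·√[p(1−p)/(n−1)].
- Subject-clustered ratio estimator: p ± t(m−1)·√[(m/(m−1))·Σ(y − pk)²]/n.

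With one site per child the two are algebraically identical.

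**5. Illustrations (invented data).**

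- *Two sites each*, 38/7/5 children with both/one/none closed, so 83/100. Unadjusted: SE √(0.83×0.17/99) = 0.0378, interval 75.5–90.5%. Clustered: Σ(y − pk)² = 38×0.34² + 7×0.66² + 5×1.66² = 21.22, SE √(21.22×50/49)/100 = 0.0465, interval 73.6–92.4%, which is 25% wider.
- *Mostly single-site (40/8/2)*, 51/62 closed: 34 of 40 single-site children; two-site children 6 both, 1 one, 1 none; three-site children 1 all, 1 one of three. Unadjusted 72.5–92.0%; clustered 71.2–93.3%, 13% wider.

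**6. Coverage.** Beta-binomial simulation, 50 children, site rate 83%. Entries are coverage of the nominal 95% interval, unadjusted t / clustered. A rerun with another seed agreed within about 0.3 percentage points.

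| Mix | ICC 0.1 | ICC 0.3 | ICC 0.5 | ICC 0.7 | Clustered wider by (ICC 0.3–0.7) |
|---|---|---|---|---|---|
| 40/8/2 | 94.8 / 94.4 | 93.5 / 94.0 | 92.5 / 93.6 | 91.6 / 93.3 | 6–14% |
| 30/12/8 | 94.9 / 93.6 | 92.6 / 93.0 | 90.8 / 92.8 | 88.4 / 92.1 | 13–28% |
| two each | 93.8 / 93.8 | 91.5 / 94.1 | 88.9 / 94.1 | 86.6 / 93.5 | 15–32% |
| three each | 92.3 / 94.0 | 87.2 / 93.7 | 82.5 / 93.5 | 78.2 / 93.4 | 28–58% |

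At ICC 0 in these mixes the clustered interval covers 93.5–94.1% and the t interval 94.6–95.7%. The normal-approximation interval is not tabulated: at 78 sites its coverage is 91% even at ICC 0, so part of its shortfall is discreteness.

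**7. After the primary gate.** The primary needs all sites closed in at least 32 of 50 children. At a true site rate of 50%, the chance of passing both the primary and this endpoint in the 40/8/2 mix is 0.77/1.18/1.66% unadjusted against 0.68/1.01/1.27% clustered (ICC 0.3/0.5/0.7). In the mixes run, the two methods disagree after the gate in at most about 0.4% of runs at 50% and 0.1% at 83%. The further gate from the first ranked secondary was not modelled.

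**The case against.** **No result of this study changes.** With one subject and listings only, neither interval will be computed. This stands. It limits the practical effect but does not make the written analysis correct.

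**The text never says that sites are independent.** This stands: 12.3.1.2 names only a t-distribution, and 12.3 calls itself a general summary. Independence is the natural reading of that silence, but every unadjusted figure above depends on it.

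**The remedy is not free.** At ICC 0.1 the clustered interval covers less than the t interval in both mixed-site scenarios, and at ICC 0 it covers less in every multi-site mix. In the mostly single-site mix the gain is 0.5 percentage points at ICC 0.3 and 1.7 at ICC 0.7, still short of 95%. The largest effects need three sites in every child, and nothing in the protocol suggests that this is typical.

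**A reader might infer that the plan's Type I error is inflated.** Tested alone at a 50% site rate, the unadjusted method has a one-sided error of 3.7–11.3% over these scenarios, against a nominal 2.5%. The documents do not support presenting those as error rates of the plan, because this endpoint is tested only after the primary and the first ranked secondary succeed. After the primary gate alone, the error is at most about 1.7% in the multi-site mixes. With one site per child it is 3.25% by either method (P(X ≥ 32 | 50, 0.5)), which comes from the primary's own rule and not from clustering.

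**Conclusion.** The point holds as a limited, low-priority one. As written, the pooled interval and p-value for the second ranked secondary make no allowance for several sites in one child, and no document supplies a method.

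For an ICC of 0.3–0.7, coverage of the nominal 95% interval falls to 91.6–93.5% (40/8/2), 88.4–92.6% (30/12/8), 86.6–91.5% (two each) or 78.2–87.2% (three each, an extreme). Clustering brings it to 92.1–94.1%. At an ICC of about 0.1 the shortfall is negligible or reversed in the mixed-site cases, and with one site per child nothing changes. Site mix, ICC, site rate and the reading of the t interval are all assumed.

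The harm is to the reported interval and p-value, not materially to pass/fail. The primary, the first and third ranked secondaries and the by-site summaries are unaffected. The point matters only if the protocol's analysis is used.

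The conflict between 12.3.3 and the other sections on imputation is a separate contradiction. It needs no assumption and lends no support to the clustering point.

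**What to change.** In 12.3.1.2 and 12.3.1.3, state that the unit of the pooled analysis of the second ranked secondary is the site, and name one subject-clustered method for its interval and p-value. Either of these would serve:

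- the ratio estimator with the subject as cluster and t on subjects − 1 degrees of freedom;
- GEE with a small-sample correction.

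Both target the site-level rate.

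Separately, in 12.3.3 restrict the no-imputation sentence to the continuous ranked secondaries, so that it agrees with the Synopsis, 12.3.1.2 and Table 8.

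The cost is wording in three sections, and a few lines of code only if the analysis is ever run. The SAP memo needs no new output. Intervals become about 6–58% wider under the assumed mixes with ICC 0.3–0.7, and coverage is slightly lower in some mixes if the ICC is about 0 to 0.1.

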- The averaged percent area closed per subject will be calculated as, “Sum of percent area closed across treatment sites for a subject/the number of treatment sites on that subject”
- The percentage of StrataGraft treatment sites with confirmed complete wound closure without autograft placement on or before Week 12 will be calculated as  $[(\text{Total number of StrataGraft treatment sites with confirmed complete wound closure without autografting on or before Week 12})/\text{Total number of treatment sites}] \times 100$

- The averaged percent area of StrataGraft treatment site per subject autografted by Week 12 will be calculated as (Sum of averaged percent area of StrataGraft treatment sites autografted for a subject/the number of StrataGraft treatment sites on a subject). It is a cumulative sum of percent area autografted for all nonmissing visits on or before Week 12.

For continuous efficacy endpoints, missing data will not be imputed. Missing or incomplete binary variables will be imputed as failures.

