### **10.3. Treatment Days 7, 14, and 21 ( $\pm$ 2 days), Day 28 ( $\pm$ 3 days), and Weeks 5 - 11 ( $\pm$ 3 days)**

Subjects will be assessed weekly until complete wound closure of study treatment site(s) is/are confirmed. The following assessments or procedures will be performed at those visits:

- Obtain vital signs (Section 11.2.4).
- Remove all dressings and expose study treatment site(s). Reapply dressings, if necessary, after all wound assessments are complete.
- Photograph all study treatment site(s) (Section 11.3.4). Photographs may be taken by study site personnel, or by trained caregivers if the subject is not able to attend the study site.
- Assess each study treatment site for:
  - Signs and symptoms of infection and, if infection is suspected, assess and treat as outlined in Section 11.3.6 and Section 11.9.1.5.
  - The percent re-epithelialized of the study site until complete closure is noted (Section 11.3.2).
  - Autograft placement on study treatment site since last study visit, noting area autografted, if any; placement is assessed until complete closure is noted (Section 11.3.3).
  - Complete closure and, if closed, confirm the maintenance of closure at the next visit (Section 11.3.2). After the first observation of closure, confirmation of wound

closure will be done at a second visit at least 2 weeks after initial observation but no later than Week 20.

- Assess pain at the study treatment site(s) using the EVENDOL (observer or parent) or FPRS (subject) rating scale (Section 11.7).
- Document reason(s) for continued hospitalization if subject has not been discharged (Section 11.8).
- Update any changes to concomitant medications and/or procedures, including any readmission to hospital related to the study wound(s) or scar management measures (Section 11.4).
- Abstract from the medical record results of any safety laboratory results (ie, CBC with differential and CMP) performed since prior visit (Section 11.5). If no recorded values in medical record from Day 28 through Week 11, samples for CBC with differential and CMP may be collected during a clinically necessary venipuncture. Only 1 post-baseline sample per subject is needed.
- PRA and anti-BSA antibody samples may be collected at any visit after Week 6, but only if they may be collected during a clinically necessary venipuncture (Section 11.6). Only 1 post-baseline sample per subject is needed.

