### **11.3.3. Area of the Study Sites Autografted**

The area of each StrataGraft treatment site that is autografted will be measured during the autografting procedure. Details about obtaining wound measurements is provided in the Manual of Procedures.

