### **12.3.3. Handling of Missing Data**

Subjects will be encouraged to return to clinic for each scheduled visit. Direct observation of the wound and collection of data at scheduled times is essential to ensure the quality of the data. However, should a visit be missed, thereby resulting in missing data for that visit, the following approaches will be employed to manage the missing data.

For the primary efficacy endpoint, missing/incomplete data will be imputed as failure (ie, no confirmed complete wound closure).

For the ranked secondary endpoints, missing/incomplete data will not be imputed.

A full description of missing data imputation methods for all endpoints will be described in detail in the SAP.

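### Ranked secondary 3 (treated area autografted by Week 12) has two conflicting derivation rules, and neither reliably gives the percent of a site autografted

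*Combined protocol and SAP*

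**What the plan says.** The endpoint is named in the Synopsis and in protocol Sections 5.2 and 12.3.1.2 as a mean, over subjects, of the averaged percent area of treatment sites autografted by Week 12. Table 8 tests it against 50%.

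Section 12.3.1.2 derives the subject value as ("Sum of percent area of StrataGraft treatment sites per subject autografted by Week 12/the number of treatment sites on that subject") and then adds: "It is a cumulative sum of percent area autografted for all nonmissing visits on or before Week 12". The Synopsis repeats the cumulative-sum sentence, but its numerator is described as already averaged before division by the number of sites: "Sum of averaged percent area of StrataGraft treatment sites autografted for a subject/the number of StrataGraft treatment sites on a subject".

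The quantities being summed are increments. At each visit the site records "Autograft placement on study treatment site since last study visit, noting area autografted, if any; placement is assessed until complete closure is noted" (Section 10.3, with a matching item in Section 10.4), and under Section 11.3.3 "The area of each StrataGraft treatment site that is autografted will be measured during the autografting procedure".

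Earlier in Section 12.3.1.2, in a paragraph covering the ranked secondary endpoints together, stands a second rule: "If a subject has autograft placement, the data collected after the autograft placement will be censored". It is written per subject, does not say which endpoints it governs, and does not appear in the Synopsis.

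No text in the documents caps a site at 100%, limits the sum to area not grafted before, or says how a re-graft is handled.

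**The concern.** A percent of a site autografted should lie between 0 and 100. A sum of per-procedure areas has that property only if no area is grafted twice. If a graft is lost and the same area is grafted again before Week 12, the literal sum counts it twice.

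The censoring sentence would prevent this, but it brings the opposite fault. If it covers this endpoint, the sum ends at the child's first graft. A later graft to new area on that site, or to another of the child's up to three sites, then disappears.

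So two programmers could follow Section 12.3.1.2 faithfully and produce different values for the same child. This is the only ranked endpoint that measures how much area was grafted, and reducing the need for autografting is part of the primary objective. Few children are expected to have a non-zero value, so one child can move the mean and its interval noticeably.

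**Working it through.** **No figure to reproduce.** The plan gives no expected value, SD or power for this endpoint. Its power statement (Section 12.1) is for the primary endpoint and does not bear on this point.

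**Inputs from the documents.** N = 50 (Section 12.1). Threshold 50% (Table 8). Up to 3 sites per subject (Section 7.1). More than 95% of adults closed without autografting (Section 6.2), so at most about 5% × 50 = 2.5 children grafted; I use 2. The 83% response assumption (Section 12.1) leaves 17% × 50 = 8.5 non-responders; I use 9 as a high case, since not every non-responder need be grafted.

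**Assumed.** All graft histories and the frequency of re-grafting; the documents give neither.

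**Step 1: the same history under each rule.** The subject value is the sum over sites divided by the number of sites.

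| History by Week 12 | Cumulative sum | Stop at subject's first graft | Distinct area |
|---|---|---|---|
| One site: 60%, then the same 60% | 60 + 60 = 120% | 60% | 60% |
| One site: 100%, then 30% of it again | 130% | 100% | 100% |
| One site: 30%, then the same 30% | 60% | 30% | 30% |
| One site: 60%, then a different 30% | 90% | 60% | 90% |
| Two sites: first wholly grafted, second wholly grafted at a later procedure | (100 + 100)/2 = 100% | (100 + 0)/2 = 50% | 100% |

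The sum fails in rows 1 to 3 and censoring fails in rows 4 and 5. A 100% cap would not repair the sum: row 3 stays at 60% and is still double counted.

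**Step 2: effect of one re-graft on the mean and SD.** Two of 50 children are grafted at 60%, one site each. SD = √[(Σx² − n·mean²)/(n − 1)]; the 95% CI is t-based with 49 df (t ≈ 2.01).

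- No re-graft: mean = (60 + 60)/50 = 2.4%. SD = √[(7,200 − 288)/49] = 11.9. CI about −1.0 to 5.8%.
- One child fully re-grafted, literal sum: mean = (120 + 60)/50 = 3.6%. SD = √[(18,000 − 648)/49] = 18.8. CI about −1.7 to 8.9%.

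The mean rises by 50% and the SD by about 58% (18.8/11.9). With 4 grafted children the mean goes from 4.8% to 6.0% (+25%); with 8, from 9.6% to 10.8% (+12.5%). Each full 60% re-graft adds 60/50 = 1.2 points.

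**Step 3: effect of censoring on the mean.** Two of 50 children are grafted 60% and later a different 30%. Distinct area gives (90 + 90)/50 = 3.6%. Stopping at the first graft gives (60 + 60)/50 = 2.4%, one third too low.

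**Step 4: can the test against 50% change?**

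- Nine children, all grafted 60% twice on the same area: literal sum 21.6% (CI 8.4 to 34.8); distinct area 10.8% (4.2 to 17.4). Both upper limits are below 50%.
- Nine children, all wholly grafted twice: literal sum 36.0% (13.9 to 58.1); distinct area 18.0% (7.0 to 29.0). Here the literal sum would miss a success that distinct area shows.

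**The case against.** A reader might infer that the plan certainly double counts re-grafts. The documents do not support that. The censoring sentence stands in the same section, and if it governs this endpoint, 60% followed by the same 60% scores 60%. What survives is the conflict. Applied here, censoring leaves a cumulative sum over visits almost nothing to accumulate, so it reads more naturally as aimed at the closure endpoints. The plan does not say so, however, and the Synopsis gives the sum with no censoring at all.

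A second objection is that a running total is a coherent measure. A repeat graft is another autograft, and the objective concerns the need for autografting and donor-site harvest. That is fair for total autograft burden, where a value above 100% is meaningful. But the endpoint is labelled as a percent of site area, and the plan does not say that burden is meant. Both can be reported if they are kept apart.

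Third, some material cannot be seen. Section 11.3.3 leaves measurement detail to the Manual of Procedures, and the SAP memo lists an additional-autografting form (Listing 16.2.5.6) whose fields are not shown. Overlap may already be captured there, so the need for a new data field is conditional. The gap in the written derivation is not.

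Fourth, the bias from double counting is conservative, the endpoint is last in the hierarchy, and no formal analysis will be run. All of this stands and sets the size of the point.

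**Conclusion.** The point holds as a definition conflict of minor weight. Section 12.3.1.2 contains two rules that give different answers. The cumulative sum overstates when the same area is grafted again; the censoring sentence, if it applies, understates when new area or another site is grafted later.

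The consequence lies in the estimate and its interval: 2.4% against 3.6% for the mean, and 11.9 against 18.8 for the SD, in the example with 2 of 50 children grafted. These figures rest on assumed graft histories.

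It would be tempting to conclude that the test against 50% is unsound. The calculations do not support that. Double counting raises the grafted area and so works against showing a mean below 50%, and it altered the result only in the extreme case of nine children wholly grafted twice. Censoring errs the other way, but with few grafted children the mean stays far from 50%.

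Nor is any present result wrong. The SAP memo states that one subject was enrolled and that only listings will be produced. The correction matters for the protocol of record and for any reuse of this endpoint.

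**What to change.** In Section 12.3.1.2 and the Synopsis:

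1. Replace the cumulative-sum sentence with a definition by distinct area: for each site, the percent of the Day 1 treated area that received autograft at least once by Week 12, ranging from 0 to 100%, with area grafted again not added again. The subject value is the mean over that subject's sites. Use the same formula in both places, so that the Synopsis no longer divides an already averaged quantity by the number of sites.
2. State that the post-autograft censoring sentence applies to the closure endpoints and not to this one.
3. Record newly grafted area and re-grafted area separately at each procedure, if the autograft form does not already do so. A yes/no re-graft flag would not be enough, because one procedure can cover both.
4. Report re-grafts separately as a measure of total autograft burden.

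The cost is two or three sentences and at most two area fields on an existing form, with no extra subjects, visits or procedures. With only listings planned, nothing needs to be re-run.
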